4.5 Dropout and management of cases

Dropout cases are defined as all the subjects who had completed the informed consent form and are screened and qualified to enter the randomized trial, regardless of when or for reasons, but have not completed the observation period specified by the study.

When the subjects drop out, the researchers should contact the subjects as much as possible by visiting their home, making follow-up appointments, telephone calls, and letters to ask the reasons, record the time of the last medication, and complete the evaluation items that can be completed.

For patients who withdraw from the study due to adverse events or ineffective treatment during the study, researchers should take corresponding measures according to the actual situation of patients.

The study data of the dropped cases should be properly preserved, not only for archival purposes, but also for the statistics of the full analysis set. No additional information is required for drop-out patients.

5. Intervention

5.1 Health education

- (1) Increasing dietary fiber intake of vegetables, such as the cruciferous food;
- (2) Reducing the intake of red meat and processed meat products;
- (3) To give up smoking and drinking;
- (4) Body weight control;
- (5) Reasonable physical exercise.

5.2 Grouping and medication

SBG group: SBG granules (provided by Jiangyin Tianjiang Pharmaceutical Co., LTD), orally, 1 sachet once, diluted in 150-200 ml of boiling water, 2 times a day.

Placebo group: Placebo (provided by Jiangyin Tianjiang Pharmaceutical Co., LTD), 1 sachet once, diluted in 150-200 ml of boiling water, 2 times a day.

5.3 Duration of treatment

In the first year, the trial granules will be started after enrollment for 3 months; In the second year, the trial granules will be started in the first 3 months; Each participant should have completed 6 months of trial granules.

5.4 Composition of Shenbai Granules

Chinese name (pinyin name)	Latin name	Original plant and medicinal part	Dose (g)
Ku Shen	Sophorae flavescens radix	Dried root of Sophora flavescens Ait.	4.5
Bai Hua She She Cao	Hedyotis diffusa	Dried whole plant of Hedyotis diffusa Willd.	10
Dang Shen	Codonopsis radix	Dried root of Codonopsis pilosula (Franch.) Nannf.	7.5
Bai Zhu	Atractylodis macrocephalae rhizoma	Dried root and stem of Atractylodes macrocephala koidz.	6
Yi Yi Ren	Coicis semen	Dried mature kernel of Coix lacryma-jobi L.Vra. mayuen (Roman.) Stapf.	10
Huang Lian	Coptidis rhizoma	Dried root and stem of Coptis chinensis Franch.	1.5
Wu Mei	Mume fructus	Dried near-ripe fruit of Prunus	4.5

		mume (Sieb.) Sieb.et Zucc.	
Pao Jiang	Zingiberis rhizome praeparatum	Fried product of the dried root and stem of Zingiber officinale Rose.	3

According to the recommended prescription of [name], the master of TCM.

5.5 Composition of placebo

It contains 5% SBG content, and the remaining ingredients are flavoring agents, starch and coloring agents. It is the same with SBG in appearance, smell and dosage form.

5.6 Drug packaging, distribution, storage and label

- (1) The SBG and SBG mimetic agents used in the study are uniformly produced by Jiangyin Tianjiang Pharmaceutical Co., LTD. The special personnel of the research group will conduct drug management. The drug receipt form are signed by two people in duplicate.
- (2) Drugs should be stored at room temperature, away from light, dry, and kept by special personnel, special counters, and locked.
- (3) The doses are packaged in one medium package for each visit use, and in one large package for all visits. The special label for investigational study should be applied to identify the investigational drug. The labels must bear the information of “For clinical trial use only”, and include the drug name, drug number and other information.
- (4) The distribution and recovery of each drug should be recorded on a special record sheet.
- (5) At the end of the study, the remaining drugs will be collected, and the drug recovery sheet should be signed by both parties. They should be handed over to the principal investigator after study.

Drug No.: _____
 
A multicenter, double-blind, randomized, placebo-controlled clinical trial of Shenbai Granules in reducing recurrence of colorectal adenoma (Project number: 2017YFC1700602) (For clinical trial use only)
 
Usage and dosage: 1 bag once, diluted in 150-200 ml of boiling water. 2 times a day
 
Dosage form: Granule formulation
 
Product batch No.:
 
Production date:
 
Storage: Sealed and kept in a cool and dry place
 
Jiangyin Tianjiang Pharmaceutical Co., LTD

--

5.7 Toxic and side effects of SBG and drug contraindications

- (1) The Chinese herbs used in SBG are all included in the *Pharmacopoeia of the People's Republic of China*.
- (2) The doses used are all within the range prescribed by the *Pharmacopoeia of the People's Republic of China*.

- (3) *Sophorae flavescens* radix and *Coptidis* rhizome are big bitter cold. Overdose is easy to damage the spleen and stomach, so patients who have deficiency and cold of spleen and stomach should not be included.

5.8 Rules for concomitant medications

In addition to trial granules, physicians should ask patients to bring in all medications they are taking at follow-up visits during the observation period to check for concomitant medications. The name of the drug (or other treatment), the amount, the frequency and duration of use of the drug or other treatment that must be continued for a co-morbid condition must be recorded in the study's medical record for analysis and report in the summary.

Medications with potential for the treatment of CRA (aspirin, folic acid, vitamin D, calcium) were prohibited.

6. Observation indicators

6.1 General observation

- (1) Demographic characteristics: sex, age, job, address, phone, etc.
- (2) Vital signs: temperature, resting heart rate, respiration, blood pressure (systolic pressure, diastolic blood pressure).
- (3) Chronic disease related information.

6.2 Effectiveness indicators

(1) Primary indicator

Adenoma detection rate (ADR): the ratio of the number of patients with new adenoma detected by colonoscopy to the total number of cases in this group during follow-up for 2 years.

(2) Secondary indicator

- ① The detection rate of any polypoid lesions: the ratio of the number of patients with any polypoid lesions detected by colonoscopy to the total number of cases in this group during follow-up for 2 years.
- ② The detection rate of high-risk adenomas: the ratio of the number of patients with high-risk adenomas detected by colonoscopy to the total number of cases in this group during follow-up for 2 years.
- ③ The detection rate of sessile serrated lesions: the ratio of the number of patients with sessile serrated lesions detected by colonoscopy to the total number of cases in this group during follow-up for 2 years.

Colonoscopy will be performed around 1 year and 2 years after baseline colonoscopy. When new polyps are found, endoscopic resection will be performed immediately, and the excised tissue will be retrieved for histological examination.

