Colorectal cancer (CRC) is one of the most common malignant tumors that threaten human health, and its morbidity and mortality are increasing year by year. Colorectal adenoma (CRA) is the precancerous lesion of CRC. Endoscopy has become an important treatment for CRA. But endoscopic polypectomy does not reduce the recurrence and cancerization rate of adenoma. At present, measures such as increasing dietary fiber, smoking cessation, and appropriate supplementation of calcium and vitamin D are used to prevent the recurrence of CRA. However, there is no established chemopreventive agent for the prevention of recurrent CRA.

With the innovative development of the "preventive treatment for disease" theory of traditional Chinese medicine (TCM), the clinical and mechanism studies on the prevention and treatment of CRC have gradually become a research focus. Under the guidance of [name], a famous TCM master, our research team combined clinical practice to propose "accumulation of dampness and heat, deficiency of spleen and Qi" as the basic pathogenesis of CRA and established the TCM formula "Shenbai Granules (SBG)" (*Sophorae flavescens* radix, *Hedyotis diffusa*, *Codonopsis* radix, *Atractylodes macrocephalae* rhizoma, *Coicis semen*, *Coptidis* rhizoma, *Mume fructus* and *Zingiberis rhizome praeparatum*). The combination of the whole formula has the functions of beneficial Qi, invigorating spleen, clearing heat and dampness. Previous studies have found that Shenbai Granules could significantly reduce the recurrence of CRA and promote the apoptosis of colorectal cancer cells.

Therefore, we plan to conduct a multicenter, randomized, double-blind clinical study to enroll patients diagnosed with adenoma after colonoscopic resection. After obtaining informed consent, the treatment group will receive SBG, and the control group will receive SBG mimic as placebo. The efficacy and safety of SBG will be evaluated by adenoma detection rate (ADR) and adverse events, as well as clinical symptoms. This study aims to provide high-quality, internationally recognized, evidence of evidence-based medicine for the development of clinical guidelines.

2. Study objectives

The primary objective is to evaluate the efficacy and safety of SBG in reducing recurrence of CRA. The secondary objective is to provide high-quality, internationally recognized, evidence-based medical evidence for the clinical guidelines of TCM in the prevention and treatment of CRA.

3. Study design

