4.1 Diagnostic criteria

The criteria are established according to the *Integrated colorectal Oncology*:

Colorectal adenoma (CRA): Colonoscopy reveals colonic and (or) rectal polyps, and pathological diagnosis is adenomatous polyps, including tubular adenoma, villous adenoma, and tubulovillous adenoma.

Tubular adenoma (microscopically): Adenoma is mainly composed of mucin-secreting epithelium with varying degrees of dysplasia. The epithelium is tall columnar and arranges in a glandular tubular structure, which is separated by the lamina propria stroma. The glands are generally more regular, sometimes also can appear different degrees of branching and irregular shape. The nuclei of the epithelial cells are large and hyperchromatic, and the nuclei are pen-rod shaped and closely arranged. In mild atypia, the nuclei are arranged at the base of the epithelium, and with the increase of atypia, the nuclei shift upward to form pseudostratified structures.

Villous adenoma (microscopically): The villi are branching and growing vertically to the mucosa, the center of the villi is a central cord, and there is fibrovascular stroma. The surface epithelium is the same as that of tubular adenoma, but the general atypia is more obvious.

Tubulovillous adenoma (microscopically): The tumor tissue is composed of a mixture of glandular tubular, papillary or villous structures, of which villous or papillary structures account for 1/5-4/5 of adenomas. If the villous structure comprises less than 1/5 or more than 4/5 of the adenoma, it is

classified as tubular or villous, respectively.

[Reference]

[1] Jingyuan Fang. Integrated colorectal Oncology [M]. Beijing: People's Medical Press,2015,205-206.

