7.1 Definition

Adverse Event (AE): defined as all adverse medical events that occurred after the participant received test medicines, which may be presented as symptoms and signs, diseases or abnormalities in the laboratory test, but may not have the causality with the test medicines.

Note: In this study, AE does not include the following conditions: diseases, situations or abnormalities in the laboratory test that previously existed before the screening, or were detected but not further deteriorate; abnormalities with clinical significance in the laboratory test or in the observation that were related to the studied disease, which were not included in the AE or SAE unless the conditions of patients were more serious than the expectation judged by the investigator.

It is up to the investigator to decide whether an abnormal result of the laboratory test or other observed abnormalities is with clinical significance.

Serious Adverse Event (SAE): referring to the death, life threatening, permanent or severe disability or loss of function that occurred after the participant received the test medicines, and the participant is required to treat in hospital or extent the hospitalization time, as well as the adverse medical events including congenital abnormalities, birth defects, etc.

Significant Adverse Event: referring to any adverse events except for SAE that leads to the adoption of directed medical measurement (such as drug withdrawal, dose reduction and symptomatic therapy) and obvious abnormalities in the hematological or other laboratory tests.

Drug-related Adverse Reaction: referring to any reaction unexpected or harmful to human body that was associated with test medicines in the clinical trial. There is at least one of the reasonable possibilities for the causality between test medicines and adverse events, i.e. could not exclude the correlation.

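### A patient whose only neoplastic finding at follow-up is colorectal carcinoma is a non-event in the primary and high-risk adenoma endpoints, and the note in 7.1 could be read to keep that case out of the AE/SAE tables.

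*Combined protocol and SAP*

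**What the plan says.** Section 6.2 defines the primary indicator as "the ratio of the number of patients with new adenoma detected by colonoscopy to the total number of cases in this group" during two years of follow-up. The high-risk adenoma indicator has the same form. The nearest wider indicator, also secondary, is "the ratio of the number of patients with any polypoid lesions detected by colonoscopy".

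The only description of adenoma is in Section 4.1: "pathological diagnosis is adenomatous polyps, including tubular adenoma, villous adenoma, and tubulovillous adenoma". Section 4.3 lists current or past colorectal malignancy as a separate ground for exclusion.

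The Background (Section 1) ties the two conditions together: "Colorectal adenoma (CRA) is the precancerous lesion of CRC". It adds that "endoscopic polypectomy does not reduce the recurrence and cancerization rate of adenoma".

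The note in Section 7.1 takes "abnormalities with clinical significance in the laboratory test or in the observation that were related to the studied disease" out of adverse event recording. The exception is left to the investigator's view of severity, since the note describes these as findings "which were not included in the AE or SAE unless the conditions of patients were more serious than the expectation judged by the investigator".

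No section says how a carcinoma found at the 1-year or 2-year colonoscopy enters the efficacy analysis, and Section 6.3 lists no separate cancer outcome.

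**The concern.** The primary endpoint is a proportion in which a lower value is better. Any patient outside the numerator but inside the denominator improves the arm's result. If the only neoplastic finding is a carcinoma, the rule in 6.2 puts the patient in the same category as one with a clear colon. Carcinoma is the outcome that preventing adenoma is meant to avoid, so the misclassification runs in the wrong direction.

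The safety side does not reliably catch the case. The Background links carcinoma to the disease under study, so an investigator could apply the 7.1 note to it. Reporting would then depend on what that investigator expected, and this may differ across the eight hospitals. The same patient could be a non-event for efficacy and absent from the safety tables.

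**Working it through.** **How such a patient passes through the rules**

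1. Section 4.3 excludes colorectal malignancy at entry, so a carcinoma at follow-up is a newly detected finding.
2. Section 6.2: no new adenoma, so not in the primary numerator, but in the denominator. The high-risk adenoma indicator also requires an adenoma.
3. The polypoid-lesion indicator may catch the case, but only if the carcinoma is classed as polypoid, and only in a secondary endpoint that pools it with all other polyps.
4. Section 4.4(1) treats deterioration of polyps as a lack of effect, but as a ground for withdrawal. It is not linked to the endpoint. If the patient leaves after year 1, LOCF in Section 10.2, read literally, carries the adenoma-free result forward.
5. Section 7.1: the note may or may not be applied, at the investigator's judgement.

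**The plan's own figure**

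Inputs from Section 3.3: control rate 52%, reduction 34% (read as relative), alpha 5%, power 90%, 20% dropout. Section 10.4 makes the test two-sided.

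- Treated rate: 0.52 × 0.66 = 0.3432. Difference: 0.52 − 0.3432 = 0.1768.
- n = (1.960 + 1.282)² × (0.52 × 0.48 + 0.3432 × 0.6568) / 0.1768² = 160 per group with unpooled variance, as stated. The pooled formula gives 163.
- 160 / 0.8 = 200 per group, 400 in total, as stated.

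**Expected number misclassified**

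The documents give no carcinoma rate. Assumptions: 0.5% to 1% over two years in both arms, carcinoma independent of adenoma, all 200 per arm in the denominator. Only adenoma-free patients are affected, so the count is 200 × carcinoma rate × (1 − adenoma rate).

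| Arm | At 0.5% | At 1% |
|---|---|---|
| Placebo | 200 × 0.005 × 0.48 = 0.48 | 200 × 0.01 × 0.48 = 0.96 |
| Shenbai Granules | 200 × 0.005 × 0.6568 = 0.66 | 200 × 0.01 × 0.6568 = 1.31 |

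Divided by 200, this is 0.24-0.48 percentage points for placebo and 0.33-0.66 for Shenbai Granules. With equal carcinoma rates, the net change in the treatment difference is 0.005 × (0.6568 − 0.48) = 0.09 points to 0.01 × 0.1768 = 0.18 points, against a planned difference of 17.7. The adenoma-only rule slightly favours the arm with fewer adenomas.

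**Effect on the test (160 per group, chi-square without continuity correction)**

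- Planned effect, 55/160 vs 83/160: p = 0.0016. Adding 1, 2 or 3 carcinoma-only patients to the Shenbai Granules arm as events, and none to placebo, gives p = 0.0023, 0.0034 and 0.0049.
- Constructed borderline case, 65/160 vs 83/160: p = 0.044. One added event gives p = 0.057.

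**Effect of the fix on sample size**

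Adding a carcinoma-only rate of 0% to 2% to both arms moves the pooled sample size from 163 to 165 per group. Power at 160 per group moves from 89.5% to 89.2%.

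**The case against.** A reader might infer that the plan scores cancer as treatment success and hides it from the safety data. The documents do not support that.

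- The plan has no success category; its category is simply no new adenoma detected. Section 4.4(1) suggests that the sponsor sees progression as failure.
- A carcinoma found with an adenoma, or reported as arising in one, would still be an event. Section 4.1 is an entry criterion, not an outcome adjudication rule.
- The 7.1 exclusion is not automatic. The clause in question speaks of abnormalities and, unlike the clause before it, does not name diseases. The adverse event definition itself includes diseases. Cancer in an adenoma-recurrence trial is an obvious candidate for being worse than expected, and hospital treatment is among the seriousness elements.
- Section 10.1 leaves analytic detail to a plan affirmed before database lock.

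A reader might also multiply an assumed 0.5-1% by 200 and report 1 to 2 misclassified patients per arm. That counts patients who also have an adenoma and are already events.

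All of this limits the point without removing it. The later analysis plan may fill gaps, but 6.2 already states a ratio, and that ratio leaves the carcinoma-only patient out of the numerator. The withdrawal rule does not change it. Section 4.1 remains the only description of adenoma in the documents, and 7.1 leaves the reporting decision open.

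**Conclusion.** The gap is real and small. As written, a patient with carcinoma and no adenoma at either follow-up colonoscopy is a non-event in the primary and high-risk adenoma endpoints. Section 7.1 permits, but does not cause, omission of that case from the AE/SAE tables.

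The size rests on an assumed carcinoma rate, independence from adenoma and the planned adenoma rates. On those terms about one patient per arm is affected. A result near the planned effect would stand; only one close to the significance threshold could change. The case for acting is the direction of the misclassification and the visibility of the worst disease outcome, not power. It is a minor correction.

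**What to change.** **Section 6.2 and the synopsis, before unblinding.** Define the primary event as *new adenoma or colorectal carcinoma* and the high-risk event as *high-risk adenoma or colorectal carcinoma*. Keep the adenoma-only definition as a sensitivity analysis.

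**Section 7.1.** State that the disease-related exclusion does not apply to colorectal carcinoma. Each case found after first dose is then recorded as an AE and assessed for seriousness under the protocol's own criteria. A blanket rule making every carcinoma after randomisation an SAE would not fit, because 7.1 counts events from receipt of the test medicines and sets its own seriousness criteria. Separately, list all carcinomas found after randomisation by arm, so that none is lost between randomisation and first dose.

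**Cost.** No extra procedure or patient is needed: the visit flow chart already has histology at 12 and 24 months. The endpoint label becomes slightly wider than the recurrent-adenoma rate behind the 52% planning figure, with the sample size essentially unchanged. The change is a protocol amendment and needs ethics approval under Section 11.1.

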6.3 Safety indicators

- (1) Physical examination at each visit.
- (2) Laboratory test: Blood routine, urine routine, liver function (alanine aminotransferase, aspartate aminotransferase), renal function (serum creatinine, blood urea nitrogen) will be rechecked before clinical intervention, every visit after taking medicine.
- (3) Adverse events: recording the conditions of adverse events occurring in the whole process from before and after the treatment, and in the observation period.

7. Adverse events

7.1 Definition

Adverse Event (AE): defined as all adverse medical events that occurred after the participant received test medicines, which may be presented as symptoms and signs, diseases or abnormalities in the laboratory test, but may not have the causality with the test medicines.

Note: In this study, AE does not include the following conditions: diseases, situations or abnormalities in the laboratory test that previously existed before the screening, or were detected but not further deteriorate; abnormalities with clinical significance in the laboratory test or in the observation that were related to the studied disease, which were not included in the AE or SAE unless the conditions of patients were more serious than the expectation judged by the investigator.

It is up to the investigator to decide whether an abnormal result of the laboratory test or other observed abnormalities is with clinical significance.

Serious Adverse Event (SAE): referring to the death, life threatening, permanent or severe disability or loss of function that occurred after the participant received the test medicines, and the participant is required to treat in hospital or extent the hospitalization time, as well as the adverse medical events including congenital abnormalities, birth defects, etc.

Significant Adverse Event: referring to any adverse events except for SAE that leads to the adoption of directed medical measurement (such as drug withdrawal, dose reduction and symptomatic therapy) and obvious abnormalities in the hematological or other laboratory tests.

Drug-related Adverse Reaction: referring to any reaction unexpected or harmful to human body that was associated with test medicines in the clinical trial. There is at least one of the reasonable possibilities for the causality between test medicines and adverse events, i.e. could not exclude the correlation.

